### **Detached/Broken Sensor Wire – Severity Category**

1. Do you see the sensor wire sticking out of your skin?
  - If no, then stop
  - If yes, then ask: On a scale of 1 to 10, where 1 is very little, and 10 is severe, how would you rate your pain or discomfort
    - If 1 – 7, **then Mild AE**
    - If 8 – 9, **then Moderate AE**
    - If 10, **then Severe AE**

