- None of the expected device-related adverse events as defined in the protocol and associated documents would be life-threatening or would result in any permanent impairment of a body function or permanent damage to a body structure;
- There are no expected electrical safety risks as the device has passed the electrical safety tests as per EN45502-1 and EN60601;
- If the subject feels any discomfort during the course of the study, he/she will be able to remove the device immediately (the device is not permanent);
- The device is being used to complement, not replace, self-monitoring of blood glucose meter information, and readings are not intended to be used alone to make diabetes self-management decisions. As with the currently approved device and per intended use of similar technologies, subjects in the study will be instructed not to use the device for diabetes therapy or management;

- Subjects will be instructed to monitor their blood glucose levels as per their usual practice.

Adverse events (AE) associated with the use of the device include pruritus (severe itchiness present 48 hours after removal), erythema (reddening of the skin present 48 hours after removal), and inflammation (swelling and pain, defined as 8 or greater on a 10 point scale 48 hours after removal) where the adhesive touches the skin; local infection at insertion site; and shooting pain located at the site of the sensor (defined as 8 or greater on a 10 point scale). Rarely, the sensor wire will fracture when the sensor is being inserted, worn, or removed. If a sensor breaks and no portion of it is visible above the skin, the participant will be instructed to not remove it and seek medical care from the study doctor and/or his staff.

No serious adverse events (SAE) or Unanticipated Problems (UP) are expected as a result of participation in this minimal risk study. However, AE, SAE and UP will be monitored in the following ways:

- Participants in the study will be instructed to call the study doctor's clinical research coordinator to report all AE, SAE and UP related to the use of the CGM devices. The study doctor and/or his staff will assess the severity of any health problems associated with the device, and if needed, see the patient at the study clinic to assure appropriate care.

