### Risks of CGM

When the wire-like sensor is deployed by the applicator, participants can expect a sensation similar to a needle insertion for a blood draw. Risks of CGM use include discomfort during sensor insertion, along with pain, inflammation, redness, swelling, minor bleeding and minor infection at the sensor insertion site. Participants might also experience these symptoms as a result of contact between the adhesive pad of the sensor and the skin. In rare cases, an infection can spread to other parts of the body.

Allergic reactions can develop in response to the sensor, the adhesive, and other parts of the CGM. If these symptoms occur, participants have the ability to remove the CGM at will and can anticipate that their symptoms will clear up within one week.

The sensor and/or applicator may fracture during use. If a sensor remains in the skin, there is minimal risk to the patient as long as a physician confirms there are no symptoms of infection or inflammation.

Patients will be advised that the investigational sensor, transmitter, and smartphone must be removed before Magnetic Resonance Imaging (MRI), Computed Tomography (CT) scan, or diathermy treatment. The device is MR Unsafe. Participants should not bring any portion of the device into the MRI environment. The Dexcom IUO CGM System has not been tested during MRI or CT scans or with diathermy treatment. The magnetic fields and heat could damage the device, causing it to stop displaying glucose readings, display inaccurate glucose readings, or prevent alerts.

Patients will also be advised of CGM system warnings that may affect the proper operation of the device and/or the patient's safety. These warnings will be described in the informed consent and authorization form, and in the informational materials provided to patients when they receive their systems.

Patients will be provided with a phone number for Dexcom's Technical Support. Staff for this line will be well-qualified to address any potential questions and risks associated with the investigational device. Significant or serious health risks with CGM are not anticipated.

The same precautions have been taken to code and/or encrypt the investigational system's electronic data as have been taken with the commercial Dexcom devices. Regardless, throughout the program, patients will be advised not to rely on the device to make any treatment decisions, and to measure their blood glucose in order to confirm any symptoms of hypoglycemia.

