## 23. Appendix B

### Adverse Events Severity and Relatedness Questions

May 2017

When patients share a complaint, program coaches will identify the complaint in the Anticipated Complaints Guidebook. Based on the complaint type, coaches will then ask questions to determine:

1. Severity of the complaint (e.g., Mild, Moderate, or Severe), and
2. Relatedness of the complaint to the use of program devices (e.g., Not Related, Probably Not Related, Possibly Related, and Probably Related)

Coaches will document answers in the templates provided, including the Adverse Event document.

If the complaint falls in any of the severity categories highlighted in red, the coach will make a “warm transfer” to the study doctor and/or his staff so that the patient can be scheduled for an ancillary appointment.

If the complaint is an emergency, patients will be instructed to call 911.

If a patient has a complaint that is not listed in the Anticipated Complaints Guidebook, the coach can “warm transfer” the patient to the study clinic for guidance. The coach will document as much as possible in Adverse Event document. Follow up with the clinic will determine severity and relatedness.

Coaches will contact the PI when situations arise that are not covered in the Anticipated Complaints Guidebook.

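### The coach script for a broken sensor wire stops when no wire is visible, where Section 9 calls for a do-not-remove instruction and referral to the study doctor

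*Combined protocol and SAP*

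**What the plan says.** Appendix B (Adverse Events Severity and Relatedness Questions) has the coach find the complaint in the Anticipated Complaints Guidebook and then ask scripted questions. The warm transfer to the study doctor carries a condition: "If the complaint falls in any of the severity categories highlighted in red". Documentation does not depend on that condition: "Coaches will document answers in the templates provided, including the Adverse Event document". For a complaint that the Guidebook does not list, the coach can transfer the patient to the clinic, and "Follow up with the clinic will determine severity and relatedness".

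The script headed Detached/Broken Sensor Wire – Severity Category has one gate question: "Do you see the sensor wire sticking out of your skin". A yes leads to a pain rating, graded Mild at 1 to 7, Moderate at 8 to 9 and Severe at 10. The other answer reads "If no, then stop". The relatedness item that follows has a single outcome (probably related) and prescribes no action.

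Section 9 (Assessment of Safety) covers the not-visible case directly: "If a sensor breaks and no portion of it is visible above the skin, the participant will be instructed to not remove it". The sentence continues, so that the participant is to be "instructed to not remove it and seek medical care from the study doctor and/or his staff". Section 12 (Risks of CGM) adds, with infection and inflammation as the symptoms meant: "If a sensor remains in the skin, there is minimal risk to the patient as long as a physician confirms there are no symptoms".

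**The concern.** Section 9 singles out one broken-wire situation for a specific instruction, and that is the situation in which the coach's script ends. A coach who follows Appendix B as written asks the gate question, hears that nothing is visible, and has no line telling the patient to leave the fragment alone and no severity-based reason to transfer the call.

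The patient most exposed is one with few symptoms, who has little reason to press the matter. That patient may try to remove a fragment, or may not reach the physician's check on which Section 12 rests its risk statement. Coaches may also differ in what they do after the script stops. This is a point about safety conduct; no endpoint or analysis is affected.

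**Working it through.** The plan states no figure on this point, so the check is to trace one case through the texts: the sensor has broken and nothing shows above the skin.

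1. **Section 9.** Trigger: broken sensor, no visible portion. Action: do not remove it; seek care from the study doctor or staff. The action does not depend on pain.
2. **Appendix B, broken-wire script.** The gate question is answered no, and the script stops. No pain score is asked, no grade is given and no instruction is supplied.
3. **Appendix B, transfer rule.** Transfer follows from a red severity category. The no branch assigns no category, so the rule cannot apply. Any loss of colour in the review copy is therefore immaterial.
4. **Section 12.** Minimal risk for a retained sensor depends on a physician's confirmation. The no branch provides no route to it.

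Coverage by branch:

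- Wire visible: 7 scores Mild (1–7) + 2 Moderate (8–9) + 1 Severe (10) = 10 of 10 graded.
- Wire not visible: no score asked, none graded.

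The next question is whether stopping before any grade is simply how Appendix B works. Two other scripts also do it. In the infection script, a no at the first question stops, but there it means that the patient sees no signs of infection. In the bleeding script, both paths can stop ungraded, but only when the blood spot is no larger than a nickel. In those scripts the stop answer marks an absent or minor problem. In the broken-wire script the complaint has already been classed as a detached or broken wire, so no covers two different states: the wire came out whole, where stopping is reasonable, or a fragment lies under the skin, which is the Section 9 case. The script does not separate them.

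On frequency, the documents support only a planned exposure. Ten weeks is 70 days; 70 / 10 days per sensor = 7 sensors; 500 participants × 7 = 3,500 sensor wears if everyone completes. Section 9 calls fracture rare without a rate, and the share with no visible portion is not given. The number of cases cannot be derived.

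**The case against.** The strongest reply is that Appendix B is a grading aid, not the care pathway. Section 9 describes it as assessment guidance for coaches and points to Appendix C for the reporting process. On that reading, stopping means only that there is no severity grade to record. Section 9 also does not say who gives the do-not-remove instruction, and Section 12 says that device warnings appear in the consent form and patient materials.

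Other duties cover part of the gap. Under Section 6 (Integration with patient care), a coach who hears of a potential study-related health concern must work to get the patient to the study doctor by warm transfer or callback, whatever the grade. A wire possibly left under the skin fits that description. Section 8 tells patients with device-related medical concerns to contact the study doctor or staff. Section 9 has participants call the research coordinator, has coaches connect patients who report events, and passes on reports made to the manufacturer's technical support. The Guidebook and the Appendix C chart are not in the copy reviewed and may add handling.

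Much of this stands. A reader might infer that these patients are denied care or that their events go unrecorded. The documents do not support that: the Section 6 duty remains in force, and coaches document answers whether or not a grade results. What the reply does not do is reconcile the script with Section 9. None of the general duties shown supplies the do-not-remove instruction. The transfer option for unlisted complaints does not clearly apply, because this complaint has its own script. A general duty is also a weak remedy when the specific script tells the coach to stop.

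**Conclusion.** The conflict holds and should be fixed. On the no-visible-wire branch, Appendix B omits the instruction not to remove the sensor and points away from the referral that Section 9 specifies for that case. Confidence is high for the mismatch in wording. It is lower for the practical consequence, which depends on how coaches apply the Section 6 duty and on what the Guidebook, Appendix C and the patient materials say.

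The extent is one branch of one script. Cases are probably few, given that fracture is described as rare, but the documents do not allow a count.

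**What to change.** In the Detached/Broken Sensor Wire severity script, replace the stop on the no branch with:

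- If no, ask whether the sensor broke and part of the wire could still be under the skin.
- If yes or unsure: tell the patient not to remove it, document the report in the Adverse Event document, and warm transfer to the study doctor or staff whatever the pain score. The clinic determines severity and relatedness.
- If the wire came out whole: stop.

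The cost is one follow-up question, two routing lines and a short note to coaches. Section 9 already contains the instruction and the referral, and Appendix B already provides the document, the transfer and the clinic's determination. No new adverse event category or procedure is needed, and design, endpoints and analysis are unchanged. If the Guidebook or the Appendix C chart already carries this handling, the script should still be brought into line with it.

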### **Detached/Broken Sensor Wire – Relatedness Category**

1. Where is the location of the broken sensor wire?
  - If in the same location as the sensor, then Probably Related (no other logical choice)

# Clinical Oversight & Adverse Event Reporting

## 24. Appendix C
